## Sample size calculation.

In order to have an impact on common practice, we would define a significant treatment effect as a 25% reduction in time to PRAM of 3. In order to demonstrate this effect with a power of 80% and a 5% chance of a type 1 error, we need an estimate of mean time to PRAM of 3 plus standard deviation from previous published work. Unfortunately, there is very little published information to act as a guide. The only published pediatric study that provides relevant data is a pilot study by Basnet et al.[17] Using only 10 patients in each arm, they showed BiPAP reduced time in ICU (48+/- 16 hrs vs. 36+/-14 hrs). They used a clinical score to guide management but it was different to the PRAM. If we take the higher of these standard deviations as a rough guide to the average ICU admission time and combine it with a power of 80% and type 1 error risk of 5%, we will need 26 patients in each arm to detect a 25% reduction in time to PRAM of 3. It must be emphasized that the shortage of relevant literature makes this only a rough estimate.

Statistical analysis.

Outcomes in the two treatment arms of the study (BiPAP and CPAP), will be compared to those in the control group (conventional acute paediatric asthma treatment). The principal end points will be analysed in the following ways:

1. Changes in asthma score over time.

The PRAM respiratory distres score is based on objective and subjective observations so the final values are non-parametric. Multiple comparisons over time, between treatment group and control, will be made with the Kruskal-Wallace test with Dunn's posthoc test.

2. Time to reach asthma score <3.

The value will be measured in hours after starting treatment so the values will be parametric. Comparison between treatment and control values will be made using t test. 3. Total number of pharmacological treatments per day.

The total number of drug treatments will be calculated for each 12 hour period. These are parametric values. Comparisons between control and treated group of repeat measures over time, will be made by analysis of variance with Tukey's post-hoc test. 4. Lung function tests.

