Standard spirometry and flow-volume loops will be performed with portable equipment in children old enough to cooperate. The main measured end point for analysis will be the change in Forced Expiratory Volume in 1 second (FEV1) over time. These values are parametric. Multiple comparisons between control and treated groups will be made by analysis of variance with Tukey's post-hoc test.

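### Items 3 and 4 use Tukey's all-pairs test although the plan states only comparisons with control; Dunnett's test would give intervals about 6% narrower

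*Combined protocol and SAP*

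**What the plan says.** The Statistical analysis text, which follows the sample size paragraph, opens by setting the contrasts for the whole analysis: "Outcomes in the two treatment arms of the study (BiPAP and CPAP), will be compared to those in the control group". The items then repeat that framing.

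- Item 3, number of drug treatments in each 12-hour period: "Comparisons between control and treated group of repeat measures over time, will be made by analysis of variance with Tukey's post-hoc test".
- Item 4, change in FEV1 over time: "Multiple comparisons between control and treated groups will be made by analysis of variance with Tukey's post-hoc test".
- Item 2, time to the target PRAM score: "Comparison between treatment and control values will be made using t test", with no post-hoc procedure named.
- Item 1, PRAM over time, uses a Kruskal-Wallis test with Dunn's test, again worded as treatment group against control.

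The aims, the Measured Outcomes list and the analysis items contain no comparison of BiPAP with CPAP. The procedure named in both items 3 and 4 is "analysis of variance with Tukey's post-hoc test"; Dunnett's test is not mentioned.

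**The concern.** With three arms there are three pairs. Tukey's procedure sets its critical value so that the error rate holds over all three, but the plan states only two: BiPAP with control and CPAP with control. Part of the 5% is therefore spent on a contrast nobody has said they will make, and the two stated contrasts are estimated with wider intervals than necessary. Dunnett's procedure is built for several arms against one control and spends the full 5% on those two contrasts. At stake is some precision on medication use and FEV1. Precision matters most for FEV1, which only children old enough to cooperate can provide.

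**Working it through.** **The plan's own figure.** The only sample size calculation is for time to PRAM 3: "a 25% reduction in time to PRAM of 3", "with a power of 80% and a 5% chance of a type 1 error". It takes 48 h against 36 h and the larger SD, 16 h, so the difference is 12 h and the standardised effect is 12/16 = 0.75. Sidedness is not stated; two-sided is assumed throughout.

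n per arm = 2 × [SD × (1.960 + 0.842) / difference]² = 2 × (16 × 2.802 / 12)² = 27.9, so 28 per arm. The plan states 26. The pooled SD, √[(16² + 14²)/2] = 15.03 h, gives 25 by the normal formula and 26 by the exact t calculation. The stated figure is thus reproduced to within two patients. It does not concern items 3 and 4 and is used below only as the source of 0.75.

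**Inputs for the comparison.** Three arms, equal allocation assumed (blocks of six). The Overview of study design projects at least 30 per arm; the sample size paragraph gives 26. Pooled error df = 3n − 3, which is 87 at n = 30 and 75 at n = 26. The family is taken as the arms at a single time point.

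**Critical values, two-sided 5%.**
- Tukey: c = q(0.95; 3, df)/√2.
- Dunnett: c solves P(|T₁| ≤ c and |T₂| ≤ c) = 0.95, where (T₁, T₂) is bivariate t with correlation 0.5.

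| n per arm | df | Tukey | Dunnett | Ratio |
|---|---|---|---|---|
| 26 | 75 | 2.391 | 2.254 | 1.061 |
| 30 | 87 | 2.384 | 2.249 | 1.060 |

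**Interval width.** The half-width is c × SD × √(2/n). At n = 30, √(2/30) = 0.258, giving 2.384 × 0.258 = 0.616 SD (Tukey) and 2.249 × 0.258 = 0.581 SD (Dunnett). The ratio of 1.06 does not depend on the outcome's SD or effect. It also hardly depends on n: it is 1.063 at 10 per arm and 1.061 at 15.

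**Error rate actually used.** At n = 30 the two-sided level per contrast is 0.0193 (Tukey) and 0.0271 (Dunnett). In 500,000 simulated trials under the null, family-wise error over the two control contrasts was 3.56% with Tukey and 4.96% with Dunnett at n = 30. At n = 26 it was 3.55% and 4.92%.

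**Power, as illustration only.** Borrowing 0.75 SD, the noncentrality at n = 30 is 0.75 × √(30/2) = 2.905. Power per contrast is 69.8% (Tukey) and 74.3% (Dunnett). At n = 26 it is 62.4% and 67.4%. If only 10 or 15 children per arm gave FEV1 (an assumption), it would be 23.0% against 27.3%, or 36.4% against 41.5%. For 80% power at this effect, 37 per arm are needed with Tukey and 34 with Dunnett: 3/37, or about 8%.

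**The case against.** **Tukey is valid.** This stands. It does not inflate type I error, and no false conclusion would follow from keeping it. The point is one of efficiency.

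**The restriction to control is an inference.** This also stands in part. The plan never says that control comparisons are the only ones. The background presents CPAP and BiPAP as two distinct types of ventilation and the trial randomises to both, so interest in comparing them is plausible. But the stated contrasts and the wording of all four items point one way. If the third contrast is wanted, it should be written down, and Tukey is then appropriate.

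**The calculation is not the planned analysis.** Items 3 and 4 concern measurements repeated over time, and the plan does not say whether Tukey's family covers the arms only or arms by time points. The figures above are for the simpler reading.

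**Power matters little for item 3.** Under Management of treatment groups, ipratropium, magnesium and conditional aminophylline are listed for the conventional arm only. Drug counts will therefore differ largely by allocation, and a slightly smaller critical value changes little there. This is fair; the narrower interval remains as a modest gain.

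**Stronger readings.** A reader might infer that the plan over-corrects its secondary outcomes and under-corrects its main one. The documents do not support those labels: the analysis section introduces all four items as principal end points. A reader might also infer that items 3 and 4 lose a known 4 to 5 points of power. The documents give no SD or target effect for either outcome, so that loss is only illustrative.

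**Conclusion.** The mismatch is real and minor. For the two contrasts the plan states, Tukey's test runs at a family-wise error of about 3.6% instead of 5% and gives intervals about 6% wider than Dunnett's. This rests on three equal arms, two-sided testing and a family made up of the arms at one time point. The drop from about 74% to 70% power holds only for a borrowed 0.75 SD effect with 30 children per arm, and FEV1 will have fewer.

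The absence of any adjustment for the time-to-PRAM-3 t tests may look like part of the same point. Two unadjusted comparisons with control do carry a family-wise error of about 9% (simulated, pooled error). But Tukey is not used there, and adjusting is a separate choice with a real price. At 0.75 SD with pooled error, Dunnett's test would take power per contrast from about 82% to 74% at 30 per arm, and from 76% to 67% at 26. That decision should be made openly alongside the sample size and does not follow from this point.

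**What to change.** In items 3 and 4, replace Tukey's post-hoc test with Dunnett's comparisons of BiPAP with control and CPAP with control. In the same sentence, say whether the family is the two arm contrasts alone or extends over time points, because the plan leaves this open. Item 1 is already worded as comparisons with control and item 2 is left as it is.

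The change takes a few words and no extra patients. Its cost is that any BiPAP-CPAP comparison on drug treatments or FEV1 becomes descriptive. If the sponsor wants that comparison tested, the plan should state it as a third contrast and keep Tukey.

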## **Research Methods:**

## Overview of study design:

The aim of the study is to determine if the use of NIV, for children admitted to hospital with an acute exacerbation of asthma, reduces their work of breathing, need for adjunctive medication, length of hospital stay, and need for intubation and mechanical ventilation. Study design will be prospective, randomized and controlled. The tightly fitting face mask necessary for NIV makes it impossible to make this a blinded study.

The principal enrollment criteria will be children over 2 years of age presenting to the ER with acute asthma. After diagnosis, all children are treated with standard therapy (systemic steroids plus 3 doses of inhaled salbutamol and 1 dose of inhaled ipratropium over a 1 hour period then hourly salbutamol). The principal decision between discharge track and admission track will be made at 2 hours after first steroid dose. Admission criteria are based on sequential PRAM scores.

After initial asthma treatment and observation in the emergency room, to determine which patients can be discharged home, those who need admission will be asked to join the study, then consented and randomized. There will be three treatment groups:

- BiPAP: standard steroid dose, hourly salbutamol and BiPAP at 15/5 cm H2O by face mask with rate 10 to 15/min, oxygen as needed.
- CPAP: standard steroid dose, hourly salbutamol and 8 to 10 cm H2O constant pressure by face mask, oxygen as needed.
- Conventional therapy: standard steroid dose plus hourly nebulized salbutamol, nebulized ipratropium q 6 hrly, magnesium sulphate 50 mg/kg IV (4 doses q 6 hrly), loading dose of aminophylline 6 mg/kg IV if no progress, oxygen as needed.

All children will be admitted to a small 3 bed respiratory unit. They will be closely monitored and objectively scored every 4 hours using the PRAM asthma clinical severity score (Pediatric Respiratory Assessment Measure)[18]. End points will be: time to reach room air, time to reach PRAM score <3, numbers requiring intubation and mechanical ventilation and medication use. Those children older than 5 or 6 yrs, will also perform lung function tests twice daily. Projected patient enrollment will be at least 30 in each arm. Estimated study duration is 6 months.

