#### Measured Outcomes:

- Length of time to reach a PRAM score of  $\leq 3$
- Time to room air.
- Total medication use per 12 hr period.
- Numbers failing treatment and transferred to ICU.
- Numbers in each group requiring hospital readmission within 48 hours of discharge
- Time to reach FEV1 >80% predicted in those children able to perform PFTs.

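### The listed lung-function outcome (time until FEV1 exceeds 80% predicted) has no specified analysis, and the FEV1 end point that is analysed is not in the outcome list

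*Combined protocol and SAP*

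**What the plan says.** Measured Outcomes contains a single lung-function outcome: "Time to reach FEV1 >80% predicted in those children able to perform PFTs".

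The Statistical analysis text, which follows the sample size paragraph, introduces its four items with "The principal end points will be analysed in the following ways". Item 4, on lung function, then states: "The main measured end point for analysis will be the change in Forced Expiratory Volume in 1 second (FEV1) over time". The method is: "Multiple comparisons between control and treated groups will be made by analysis of variance with Tukey's post-hoc test". Item 4 calls the values parametric. It does not give the scale (litres or percent predicted), the time points, the baseline or the handling of missing readings.

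On timing, the Overview of study design says: "Those children older than 5 or 6 yrs, will also perform lung function tests twice daily". The sentence in the Overview that lists the end points does not mention FEV1. No section describes spirometry after discharge.

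Only one time-to-threshold outcome has a named test. It is item 2, time to a low asthma score: "Comparison between treatment and control values will be made using t test".

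**The concern.** The plan defines two different end points from the same spirometry readings and does not connect them. If it is followed as written, the listed outcome is never estimated, and the result that is reported corresponds to nothing in the outcome list. Until the two are reconciled, a report could present either one and cite a section of the plan in support.

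This matters more than the position of FEV1 at the end of the list suggests. The trial is unblinded, and the plan itself describes PRAM as partly subjective. FEV1 is an instrument reading that could corroborate the score, but only if its definition is settled before the data are seen.

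**Working it through.** No figure in the plan is attached to FEV1, so the main check compares the two sections.

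| | Measured Outcomes | Statistical analysis, item 4 |
|---|---|---|
| Quantity | Time until a threshold is crossed | Repeated continuous measurement |
| Scale | Percent predicted, threshold 80% | Not stated |
| Data per child | One time, or none if the threshold is not reached | One value per test |
| Method | None | ANOVA with Tukey |
| Appears in the other section? | No | No |

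**Step 1: can an analysis of the listed outcome be found elsewhere?** The 80% predicted threshold appears only in Measured Outcomes. The t test in item 2 is written for the asthma score alone. It also needs a time for every child, which does not exist for a child who never crosses the threshold.

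**Step 2: can the item 4 result stand in for it?** No. Two arms with the same mean change in FEV1 can differ in how many children are above 80% predicted and when they got there. ANOVA on change returns neither quantity.

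**Step 3: how finely is the threshold time observed?** Twice-daily testing gives 24 h / 2 = about 12 h between tests. For scale, the pilot figures used for sample size, "BiPAP reduced time in ICU (48+/- 16 hrs vs. 36+/-14 hrs", differ by 48 − 36 = 12 h, and 12/48 = 25%. Those figures are ICU times, not FEV1 times. If an FEV1 effect were of similar size, it would equal about one testing interval, so the method must allow for the gap.

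**Step 4: who supplies the later readings?** Spirometry is described only during admission. Children leave by discharge, by ICU transfer, or by discontinuation for impending respiratory failure (Criteria for study termination). Each exit plausibly depends on recovery or deterioration, so later readings probably over-represent children who have not yet left. Item 4 has no provision for this and, unlike item 3, does not mention repeated measures.

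**Step 5: does the sample size depend on FEV1?** The target is stated as "we would define a significant treatment effect as a 25% reduction in time to PRAM of 3". The inputs are δ = 12 h, the larger SD of 16 h, 5% type 1 error (two-sided assumed) and 80% power:

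n = 2 × [σ(z₀.₉₇₅ + z₀.₈₀)/δ]² = 2 × [16 × (1.960 + 0.842)/12]² = 27.9, so 28 per arm.

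This is within two of the stated 26. With a pooled SD of √((16² + 14²)/2) = 15.03 and the t distribution, the result is 25.6, so 26. FEV1 enters neither calculation.

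**The case against.** Five points can be made on the other side.

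- **The plan limits the choice.** Item 4 designates one main FEV1 end point, and the section opens by saying that outcomes in both NIV arms will be compared with control. A reader might infer that the listed outcome will certainly go unanalysed, or that the better-looking version will be chosen. The documents support neither inference. What stands is that no analysis of the listed outcome is specified.
- **The gap is not unique.** Time to room air, ICU transfer and readmission within 48 hours also lack a named test. That is true, but those are omissions. For FEV1 the plan specifies a different end point, which makes it a contradiction.
- **FEV1 is minor.** It is last in the list, absent from the end-point sentence in the Overview, confined to children who can do spirometry, and plays no part in the sample size. This stands and limits the impact. Against it, the analysis section places FEV1 among the principal end points.
- **Change in FEV1 may be the better end point.** A threshold time discards information, and 12-hourly testing will produce ties. A reader might infer the opposite, that change is the weaker choice. Neither ranking is shown. The answer depends on age mix, baseline FEV1 and length of stay, and none of these is given.
- **Simple censoring would not repair it.** Censoring each child at the last test would treat leaving because of deterioration as uninformative. This stands, and the fix takes account of it.

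**Conclusion.** The point holds as a contradiction between Measured Outcomes and item 4 of Statistical analysis. The listed FEV1 outcome has no specified analysis, and the analysed FEV1 end point is not listed. This follows from the text alone and needs no assumption.

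The secondary point, that ANOVA on the available values does not handle the thinning of readings, is an inference. It assumes that spirometry stops when a child leaves and that leaving is related to recovery or deterioration. A reader might go further and say that later values come only from slow recoverers. With no discharge rule and no analysis time points stated, the text supports only that this becomes increasingly likely.

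A reader might also infer that FEV1 will be analysed in litres, so that body size adds noise. Item 4 is silent on scale, and the only scale the protocol gives for FEV1 is percent predicted. Any figure for such noise would need a range of predicted FEV1 that the documents do not give, and it would not measure the mismatch.

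The effect on the trial is limited to children able to perform spirometry. The documents do not give their number, so no loss of power or precision can be calculated. The change should be made, but the trial's sample size does not depend on it.

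**What to change.** Before any outcome data are examined, make Measured Outcomes and item 4 name the same main FEV1 end point. Either choice is acceptable.

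**If it is time to FEV1 above 80% predicted:**
- Measure from randomisation and compare each NIV arm with control by a time-to-event method that allows for the roughly 12-hour gap between tests.
- State how children already above 80% at the first test are handled.
- Count children who leave for ICU or deterioration as not having reached the threshold, or treat leaving as a competing event. Do not treat them as ordinary censoring.
- State the rule for children discharged home before a reading above 80%.

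**If change in FEV1 is kept, as main or supportive:**
- Add it to Measured Outcomes with its scale and time points.
- Analyse percent predicted in a repeated-measures mixed model adjusted for baseline FEV1, and say when the baseline reading is taken.
- State the model's assumption that leaving depends only on readings already observed.

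The cost is revised wording in the two sections and slightly more analysis work. The same spirometry readings serve either option, and neither the sample size nor data collection changes.

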## Inclusion criteria:

In order to avoid confusion with viral bronchiolitis, the study is open to all children over 24 months old who present to the emergency department diagnosed with an acute asthmatic attack severe enough to require hospital admission.

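### The FEV1 analysis states no scale and has no body-size standardisation; if change is analysed as a volume, as the wording literally reads, precision is lost that % predicted would keep

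*Combined protocol and SAP*

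**What the plan says.** Two places in the combined protocol and SAP define the lung-function end point, and they differ.

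- **Statistical analysis, item 4 (under the Sample size calculation heading):** "The main measured end point for analysis will be the change in Forced Expiratory Volume in 1 second (FEV1) over time". The method is: "Multiple comparisons between control and treated groups will be made by analysis of variance with Tukey's post-hoc test". No unit, % predicted, z-score, height, age or baseline term appears.
- **Measured Outcomes:** "Time to reach FEV1 >80% predicted in those children able to perform PFTs". This is a time-to-threshold outcome on a size-standardised scale. No analysis is given for it.

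Three other statements fix who contributes data.

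- **Overview of study design:** "Those children older than 5 or 6 yrs, will also perform lung function tests twice daily".
- **Inclusion criteria:** "the study is open to all children over 24 months old". No upper age is set.
- **Overview of study design:** "Projected patient enrollment will be at least 30 in each arm". This covers all ages. The size of the spirometry subset is not stated.

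The Statistical analysis section introduces its numbered items, lung function among them, as the principal end points.

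**The concern.** FEV1 is by name a volume, and where the authors wanted % predicted they wrote it. Taken as written, item 4 therefore compares changes in volume among children who may run from early school age to adolescence. Change from baseline removes each child's own starting level. It does not remove the tendency of a bigger child to gain more litres for the same proportional recovery. That extra spread sits in the error term of an analysis of variance that has nothing to absorb it.

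At stake is precision on the one instrument-based measure of airway obstruction in an unblinded trial. The PRAM is, by the plan's own account, partly subjective. Only some of the roughly 30 children per arm can do spirometry, and no sample size was set for this end point, so there is little precision to spare. Leaving the scale open also allows it to be chosen after open-label data have been seen.

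**Working it through.** **1. The plan's own figure.** There is none for FEV1: no effect, SD, power or sample size. The only stated sample size, 26 per arm, concerns time to PRAM 3: "we would define a significant treatment effect as a 25% reduction in time to PRAM of 3". A 25% reduction from 48 h is 12 h. With SD 16 h, two-sided 5% and 80% power, n = 2 × (1.960 + 0.842)² × 16² / 12² ≈ 28 per arm. This is close to 26 but does not bear on lung function.

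**2. Formula.** Let the change in % predicted have mean m and SD s. Let predicted FEV1 have coefficient of variation cv, independent of that change. Change in litres is predicted FEV1 times the change as a fraction. Scaled by mean predicted FEV1, its variance relative to the % predicted analysis is

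ratio = (1 + cv²) + (m/s)² × cv².

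**3. Inputs (all assumed; none is in the documents).** 15 children per arm; control change 25 points; NIV change 40 points (effect 15); SD 15 points; predicted FEV1 spread evenly over 1.2–2.4 L (narrow) or 1.2–3.6 L (wide). For an even spread, SD = range/√12.

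- Narrow: SD 0.346, mean 1.8, cv 0.19, cv² 0.0370.
- Wide: SD 0.693, mean 2.4, cv 0.29, cv² 0.0833.

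**4. Variance ratio.** (m/s)² is (25/15)² = 2.78 in control and (40/15)² = 7.11 with NIV.

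| | Control | NIV | Average | Efficiency (1/average) |
|---|---|---|---|---|
| Narrow | 1.037 + 0.103 = 1.14 | 1.037 + 0.263 = 1.30 | 1.22 | 0.82 |
| Wide | 1.083 + 0.231 = 1.31 | 1.083 + 0.593 = 1.68 | 1.50 | 0.67 |

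Size thus accounts for about 18% (1 − 0.82) or 33% (1 − 0.67) of the variance in litres. To recover the precision would take about 22% or 50% more children.

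**5. Power, by simulation of a two-arm t test, 15 per arm.**

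| Scale | Power |
|---|---|
| % predicted | about 75% |
| Litres, narrow | 67% |
| Litres, wide | 59% |

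A separate simulation with log-normal predicted FEV1 gave 67%, 58% and 49% in litres for cv 0.2, 0.3 and 0.4. For 80% power, n per arm is 16 on % predicted against 20, 25 and 31 in litres.

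**6. Type I error.** With no treatment effect, the test in litres rejected in 4.7% to 5.1% of simulated trials, so error control is intact.

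**7. Sensitivity.** With cv 0.2 and m/s 0.5 the ratio is 1.04 + 0.25 × 0.04 = 1.05. With cv 0.4 and m/s 3 it is 1.16 + 9 × 0.16 = 2.60. The loss can be negligible or substantial, depending on the age mix and on how uniformly children recover.

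**The case against.** The strongest reply is that no unit is stated. The only FEV1 scale anywhere in the documents is % predicted, so item 4 may have been meant on that scale. That stands in part: volume is the literal reading, not an explicit choice, and a reader who concludes that the plan has chosen litres goes further than the text. The wording still needs settling under either reading.

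Three other stronger inferences are not supported.

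- **That body size drives most of the spread.** The end point is change, and under the inputs used here size accounts for only 18% to 33% of the variance.
- **That a chance age imbalance adds a separate harm.** Under randomization it is part of the variance already counted. There is no bias.
- **That levels of FEV1 are compared in litres at each time.** Size would matter more there, but item 4 names change.

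It is also fair to say that every input is assumed, that the formula takes proportional recovery to be unrelated to size, and that the powers are for one two-arm comparison, not the planned three-group analysis with Tukey's test. The sample size rests on time to PRAM 3 alone, so the trial's main conclusion does not turn on this. These points limit the severity. They do not remove the inconsistency or the case for a size-free scale.

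**Conclusion.** The point holds as a matter of precision and specification, at low to moderate severity. Item 4 leaves the FEV1 scale unstated and unstandardised, reads literally as volume, and does not match the outcome listed under Measured Outcomes. If litres are used, the illustrative variance inflation is 1.22 to 1.50, costing roughly 8 to 16 percentage points of power in a two-arm comparison of 15 per arm. The plausible range of inflation is 1.05 to 2.6. These sizes are conditional on assumed subset size, effect, SD, mean change and spread of predicted FEV1. The documents cannot narrow them.

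**What to change.** In item 4 of the Statistical analysis section:

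1. Define FEV1 as % predicted, using one named reference equation, the same one for the outcome under Measured Outcomes.
2. Include baseline % predicted as a covariate.
3. Report differences between groups in percentage points with 95% confidence intervals, and give litres descriptively.
4. Reconcile this item with the listed outcome of time to exceed 80% predicted: either give that outcome its own analysis or state which of the two is the lung-function end point.

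The cost is mostly wording. A reference equation must be chosen, and height must be recorded; the % predicted outcome implies this, but no section lists it as collected. No extra test or patient is needed. The change should be made before outcome data are examined, since the trial is open-label.

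### Item 4 compares twice-daily FEV1 by ANOVA with Tukey's test without saying how repeated readings within a child, or early discharge, are handled

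*Combined protocol and SAP*

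**What the plan says.** The Overview of study design states: "Those children older than 5 or 6 yrs, will also perform lung function tests twice daily". Statistical analysis, item 4 limits spirometry to children who can cooperate and defines the analysed quantity: "The main measured end point for analysis will be the change in Forced Expiratory Volume in 1 second (FEV1) over time". The method is one sentence: "Multiple comparisons between control and treated groups will be made by analysis of variance with Tukey's post-hoc test".

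Item 3, on drug treatments per 12-hour period, names the same test but describes the data differently: "Comparisons between control and treated group of repeat measures over time, will be made by analysis of variance with Tukey's post-hoc test". Item 4 does not use the term repeat measures.

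The Measured Outcomes list gives a different FEV1 outcome, with one value per child: "Time to reach FEV1 >80% predicted in those children able to perform PFTs". The Statistical analysis text places FEV1 among its principal end points. The sample size does not rest on it.

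**The concern.** Readings from one child are correlated, and analysis of variance in its basic form assumes they are not. If all readings enter as separate observations, the standard error of an arm comparison is too small and chance differences are declared significant too often.

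The usual alternative, classical repeated-measures ANOVA, accounts for the correlation but needs a complete set of time points from each child. A shorter hospital stay is a stated aim of NIV. A complete-set rule would therefore remove more children from the NIV arms than from control, and would remove the quicker responders, so the arms left for comparison are no longer the randomised ones.

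The trial is open-label. If the choice between these analyses is left until the data are in, the FEV1 result will depend on a decision made with arm differences in view.

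**Working it through.** **The plan's own figures.** The plan gives no error rate, SD or within-child correlation for FEV1, so there is nothing to reproduce on this point. Its one computed figure is 26 per arm for time to PRAM of 3. With a 12 h difference and SD 16, the normal formula gives 2 × (1.960 + 0.842)² × 16² / 12² = 27.9, so 28. The FEV1 point does not bear on that number.

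**Inputs.** From the plan: three arms, twice-daily readings, 5% type 1 error (taken as two-sided), and pilot times of 48 (SD 16) and 36 (SD 14) h. Assumed, because the plan does not give them: m readings per child, within-child correlation ρ, and 15 to 30 children per arm able to do spirometry.

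**Reading A: all readings pooled as independent.** The standard error of an arm difference is too small by the factor √(1 + (m − 1)ρ). A single nominal 5% two-arm test then has true size 2 × (1 − Φ(1.96 / factor)). The last column is a null simulation of Tukey's test on pooled readings (three arms, 15 and 30 children per arm). It counts a significant result on either NIV-control contrast.

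| m | ρ | factor | two-arm test | Tukey, either NIV-control contrast |
|---|---|---|---|---|
| 2 | 0.5 | √1.5 = 1.22 | 11.0% | 10% |
| 2 | 0.7 | √1.7 = 1.30 | 13.3% | 13% |
| 4 | 0.5 | √2.5 = 1.58 | 21.5% | 24–25% |
| 4 | 0.7 | √3.1 = 1.76 | 26.6% | 30–32% |

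With independent readings the last column is 3 to 4%. It is below 5% because Tukey's cut-off also covers BiPAP against CPAP. At ρ = 0.3 the Tukey figures are about 7% (m = 2) and 16% (m = 4).

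Pooling changes from baseline does not help. For any of the three pairs, the rate is 13 to 15% with two post-baseline readings and 30 to 36% with four.

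**Reading B: one change value per child.** In simulation, Tukey's test over all three pairs gives 5.0%, so type 1 error is held. The plan does not say which change, or between which times.

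**Reading C: the arm-by-time term in an ordinary ANOVA.** The simulated rate is 0 to 2%, which is conservative. The error therefore runs in the other direction if this is the test meant.

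**Reading D: classical repeated-measures ANOVA on complete sets.** To see who would remain, I took the pilot ICU times as a proxy for time under observation and assumed a gamma shape, with shape = (mean/SD)² and scale = SD²/mean. Control is 48 h, SD 16 (shape 9, scale 5.33). NIV is 36 h, with SD 16 (the value the plan uses) or SD 14 (the pilot's own).

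| Time | Control remaining | NIV remaining, SD 16 | NIV remaining, SD 14 |
|---|---|---|---|
| 24 h | 96% | 76% | 80% |
| 36 h | 76% | 44% | 45% |
| 48 h | 46% | 20% | 18% |

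The later the last required time point, the smaller and the more unequal the analysed set. At 24 h most children in each arm are still present.

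**The case against.** The strongest reply is that item 4 never says the ANOVA is ordinary or that readings are treated as independent. Item 3 uses the same test for data it calls repeat measures, so a repeated-measures analysis may be intended throughout. A change in FEV1 could also be one value per child, for which ANOVA with Tukey's test holds its level. All of this stands. A reader might infer that the plan commits to an analysis whose false-positive rate is several times 5%. The documents do not support that: the inflation belongs to one possible reading, and under the arm-by-time reading the test is conservative.

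The size also depends on outside assumptions. With six readings per child and correlation 0.7, pooling gives about 44 to 45%. That figure should not be used here: six twice-daily readings take roughly 60 h or more, and the proxy above leaves only 21% of control and 8% of NIV children at 60 h.

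The proxy is weak too. It uses ICU time from a pilot with 10 patients per arm and a different clinical score, and the plan itself calls the resulting estimate rough. The plan contains no 48 h complete-set rule. The percentages therefore illustrate the direction of the selection and do not predict it.

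The reply does not supply the missing specification. The repeated-measures reading brings the early-discharge problem with it, and the one-value reading needs a value and a time that the plan does not give.

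**Conclusion.** The concern holds as a gap in specification with a real consequence. Item 4 does not account for repeated readings within a child or for early discharge. If readings are pooled, false positives on the NIV-control contrasts are about 10 to 13% with two readings and 24 to 32% with four, for assumed correlations of 0.5 to 0.7. If classical repeated-measures ANOVA is used, the analysed set is selected by something NIV is meant to change. A single change value per child would be sound on type 1 error, but it is not specified.

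The direction under pooling holds for any positive correlation. The exact percentages depend on the assumed correlation and number of readings. FEV1 is measured only in children old enough to cooperate and does not drive the sample size, so this is a worthwhile and cheap improvement that leaves the main comparison untouched.

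**What to change.** In item 4, and for the repeated 12-hour counts in item 3, replace ANOVA with Tukey's test by a mixed model for repeated measures. It should include arm, time, arm-by-time, a within-child covariance structure and the baseline value, and use all available readings. Report the two NIV-control contrasts with 95% confidence intervals at one prespecified early time, for example 24 h, when most children should still be in hospital.

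In the same edit, reconcile the FEV1 end point in item 4 (change over time) with the one in Measured Outcomes (time to above 80% predicted).

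The cost is SAP wording and a little more analysis work, with no new data. The downside is that the model assumes missing readings are explained by the earlier ones. Children who leave before 24 h will have few earlier readings, so the number contributing at that time should be reported by arm.
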